5.8.2 Impact of Missing Data on the Primary Analysis

5.8.2.1 Missing covariates

To calculate the primary outcome measure of the RCADS T-scores, it requires the participants sex and age. As we are collecting gender, participants that select the options of 'non-binary' or 'prefer not to say' will be considered as missing and thus not be included in the primary analysis. We do not expect any missing data regarding the age of the participant as this is used to determine eligibility.

The impact of this on the primary analysis will be assessed using multiple imputation by chained equations. The imputation model will include key baseline variables (age, gender, baseline RCADS-25 T-score, baseline CDRS-R score, and baseline BADS-SF score). A 'burn –in' of 150 will be used and 50 imputed datasets will be created. The primary analysis will then be rerun within the imputed datasets and Rubin's rules will be used to combine the multiply imputed estimates.

In addition to the above analysis, patterns of missingness of covariates amongst participants will be summarised descriptively.

5.8.2.2 Pattern mixture model

The primary analysis will use a covariance-pattern, repeated-measures, mixed-effect linear regression model, which implicitly assumes missing outcome data are missing at random (MAR). However, it is possible that participants who failed to attend their follow-ups differed from those who did attend (e.g. had worse depression and anxiety symptoms, and therefore would have scored higher on the RCADS-25 if they had attended the follow-up). This would mean the data were missing not at random and would represent a departure from the MAR assumption. The sensitivity of the primary analysis results to departures from the MAR assumption will be explored using a pattern-mixture model, implemented using the `rctmiss`

command (White (2018); White et al (2011). This command currently supports the use of fixed-effect models only, and therefore a linear regression model comparing the primary outcome at 6-months post randomisation will be used, adjusting for treatment arm, age, and sex.

The pattern mixture model works by including a sensitivity parameter quantifying the departure from the MAR assumption. For example, if we expected that those who failed to complete the follow-up at 6-months post randomisation on average would have scored two points lower on the RCADS-25 T-score than those who did attend the follow-up, the sensitivity parameter would be equal to 2. The pattern-mixture model can then be used to obtain an estimate of the treatment effect given this level of departure from the MAR assumption. The `rctmiss` command estimates the treatment effect for varying values of the sensitivity parameter ranging from zero up to any positive value, which allows for the assessment of the impact of varying degrees of departure from the MAR assumption on the treatment effect estimate.

The `rctmiss` command will be used to produce a graph of the adjusted mean difference in RCADS-25 T-scores between treatment groups for varying values of the sensitivity parameter. This will be done assuming the value of the sensitivity parameter is equal in both groups (missing data are equally informative in both groups), and also assuming the sensitivity parameter is equal to zero in the UC group and varying in the BA group, and vice versa (missing data are only informative in one group and not the other).

While the results of this sensitivity analysis will not be directly comparable to the primary analysis model, it will be able to give an indication of how sensitive the estimate of the treatment effect is to departures from the MAR assumption in the primary outcome data.

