3.4 Outcomes

3.4.1 Primary Outcome

- *Revised Children's Anxiety and Depression Scale-Brief Version:*
 - *Variable type:* Continuous.
 - *Range and polarity:* Each item can take a score from 0-3, and the total raw score ranges from 0-75. Raw scores are then converted to T-scores for the appropriate gender and school year. Derivation of T-scores are given in more detail in Section 5.3.1. Higher raw scores and t-scores represent higher levels of depression and anxiety.
 - *Timepoints:* The RCADS-25 was collected at baseline, 6 months post-randomisation and 12-months post-randomisation.

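### The pattern-mixture sensitivity analysis gives its parameter the opposite sign to the departure it is meant to test, and leaves out baseline RCADS-25, setting and site

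*SAP*

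**What the plan says.** Section 3.4.1 fixes the polarity of the primary outcome: "Higher raw scores and t-scores represent higher levels of depression and anxiety".

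Section 5.8.2.2 explains why a check beyond missing at random (MAR) is wanted. Participants who do not attend might differ from those who do; the case it offers is that they "had worse depression and anxiety symptoms, and therefore would have scored higher on the RCADS-25 if they had attended the follow-up".

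It then introduces the sensitivity parameter by an example, which is the only definition given. If non-attenders are expected to have "scored two points lower on the RCADS-25 T-score than those who did attend the follow-up, the sensitivity parameter would be equal to 2". The command is said to estimate the effect for values "ranging from zero up to any positive value". Three scenarios are to be plotted: the same parameter in both arms, and then the one-arm cases, "assuming the sensitivity parameter is equal to zero in the UC group and varying in the BA group, and vice versa". No upper limit is stated.

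Because the command takes only fixed-effect models, a linear regression at 6 months "will be used, adjusting for treatment arm, age, and sex". The primary model in section 5.7 has baseline RCADS-25, setting and site as well. Section 5.8.2.2 closes by conceding that its results cannot be compared directly with the primary model.

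**The concern.** The motivating departure and the parameter point in opposite directions. Higher is worse and the worry is about worse scores, yet a positive parameter is illustrated as a lower, better score, and only values from zero upward are described. A programmer or reader who follows the text attaches the wrong assumption to every non-zero point on the graph.

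The covariate set is a second, separate matter. A pattern-mixture analysis should start, at parameter zero, as close as possible to the assumption under test. If drop-out depends on baseline severity, a model without baseline RCADS-25 starts elsewhere, and part of what it shows as departure from MAR would be explained by a variable the trial has measured.

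Nothing else in the SAP fills the gap. The multiple imputation in section 5.8.2.1 is aimed at participants whose T-score cannot be derived because of the recorded gender, and section 5.8.3 deals with the timing of follow-up.

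**Working it through.** **Inputs.** From SAP section 3.5: loss to follow-up 23%, the mean of rates from 14% to 32%; 172 evaluable participants; design effect 1.04; target 236. From section 5.8.2.2: the example of 2 points and the three scenarios. Assumed here: a 5-point departure for illustration, and missingness by arm set at the ends of the 14% to 32% range.

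**The plan's own figure.** The design effect is 1 + (5 - 1) x 0.01 = 1.04. Then 172 x 1.04 = 178.88, and 178.88 / 0.77 = 232.3, so 233. Rounding up within each arm gives 90 / 0.77, so 117 per arm and 234 in total. This is within 2% of 236. The 23% is used as stated, and nothing here disputes the sample size.

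**Sign.** Let delta be the missing mean minus the observed mean. The feared departure is delta > 0. By the worked example, parameter p = +2 gives delta = -2, so delta = -p. With p at or above zero, delta is never positive.

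**Effect on the estimate.** In an arm with missing fraction m, the overall mean is the observed mean plus m x delta. The BA minus UC difference therefore shifts by

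m_BA x delta_BA - m_UC x delta_UC.

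This is exact for a simple difference in means and approximate after covariate adjustment. A negative difference favours BA. For a 5-point departure, in T-score points:

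| Missing BA / UC | Reading | Equal | BA only | UC only |
|---|---|---|---|---|
| 23% / 23% | as written (lower) | 0.00 | -1.15 | +1.15 |
| 23% / 23% | feared (higher) | 0.00 | +1.15 | -1.15 |
| 32% / 14% | as written | -0.90 | -1.60 | +0.70 |
| 32% / 14% | feared | +0.90 | +1.60 | -0.70 |
| 14% / 32% | as written | +0.90 | -0.70 | +1.60 |
| 14% / 32% | feared | -0.90 | +0.70 | -1.60 |

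For example, 0.23 x 5 = 1.15 and (0.32 - 0.14) x 5 = 0.90. At the SAP's own 2 points and 23% missing, the one-arm shift is 0.46.

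**The other possibility.** If the command adds the parameter to the missing mean, the computed curves are those in the feared rows. The SAP's example would then tell the reader to interpret them as non-attenders doing better. The documents do not show which convention the software uses.

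**Covariates.** Section 5.7 has arm, arm-by-time, baseline RCADS-25, age, sex, setting and site. Section 5.8.2.2 has arm, age and sex. The fixed-effects limit accounts for losing the random effects. It does not account for losing baseline RCADS-25, setting and site, which are fixed covariates.

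An illustrative large-sample simulation shows what can follow. It assumed a true effect of -5, SD 10, drop-out depending on baseline in the BA arm only, and about 23% missing in BA against 21% in UC. For assumed baseline-to-6-month correlations of 0.3, 0.5 and 0.7, the model without baseline gave -5.5, -5.9 and -6.2; with baseline it gave about -5.0 each time. The standard error without baseline is larger by a factor of 1 / sqrt(1 - r^2), that is 1.05, 1.15 and 1.40 for the same correlations. That is a matter of precision and does not affect how the estimate moves with the parameter.

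**The case against.** Both directions in section 5.8.2.2 are given as illustrations, and the general worry is only that non-attenders differ. The phrase about the range describes what the command does; the instruction itself asks for a graph over varying values and fixes no range. The lower-score example may therefore be a one-word slip, and the code may turn out right. This stands as far as intent goes. It does not remove the problem, because the example is the only definition a programmer or reader has.

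A reader might infer that the analysis can only reassure falsely, because adverse departures are never shown. The documents do not support that. All three scenarios are planned, and with equal missingness the UC-only curve as written (+1.15) coincides with the BA-only curve under the feared departure, while the equal-parameter curve is flat under either sign. The plotted values still cover both directions. What is wrong then is the assumption attached to each curve. With unequal missingness the error can also go either way: at 14% BA and 32% UC, the largest shift against BA is greater as written (+1.60) than under the feared departure (+0.70).

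A reader might also want to state the shift as a share of the target effect. That needs a trial SD for the T-score, and the SAP gives none.

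On covariates, the SAP already admits that the analysis is not directly comparable with the primary model. That is fair for the random effects and the 12-month data, which a single-time-point regression cannot carry. It neither mentions nor justifies dropping baseline RCADS-25, setting and site.

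**Conclusion.** The point holds on the SAP's own wording. Section 5.8.2.2 fears higher scores among non-attenders, illustrates a positive parameter as lower scores, and describes only values from zero upward. Either the feared departure is not examined under its own label, or the graph will be read in reverse.

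The size depends on missingness by arm. If it is equal, no value leaves the plotted range and the fault is one of labelling (plus or minus 1.15 T-score points at 23% and 5 points). If it is unequal, the results themselves change: at 32% BA and 14% UC, the equal-parameter shift is -0.90 as written against +0.90 corrected, and the largest shift against BA is +0.70 against +1.60. The 5-point departure and the arm-specific rates are assumptions; only the 23% and the 14% to 32% range come from the SAP.

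The omission of baseline RCADS-25, setting and site is a separate weakness with no stated reason that requires it. Its size cannot be fixed from the document; the simulation shows only that parameter zero need not match the primary model's MAR assumption.

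This should be fixed before the analysis. It is not a fault in the primary result: it concerns one sensitivity analysis and leaves the primary estimate untouched.

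**What to change.** In section 5.8.2.2:

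- Define delta as the mean RCADS-25 T-score in missing minus observed participants, conditional on the model covariates, with positive meaning higher (worse). The conditional wording matters, because in a covariate-adjusted model the parameter is not a raw difference in means.
- Change the example so that two points higher corresponds to +2.
- Check the software's sign convention against this definition, for instance on a small constructed dataset, and record the result.
- State the range of delta in advance. It must include the worse direction and preferably both signs, for the equal, BA-only and UC-only scenarios. The limits are for the trial team to justify.
- Add baseline RCADS-25 T-score to the regression, and setting and site where they can be estimated. If any is left out, say why.

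The cost is a few sentences in the SAP and a few lines of code. No new data are needed and no other analysis changes.

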5.8.3 Impact of timing of data collection on the Primary Analysis

For the collection of the primary outcome measure of the RCADS, a pragmatic approach is taken for data collection, whereby no definitive deadline has been made for participants to return the data at each follow-up time point. Therefore, it is possible that follow-up completion times will show some departure from the planned follow-up schedule. We will undertake the following sensitivity analyses to examine the potential influence that variation in follow-up time has on the results of the primary analysis.

We believe that a 1-2 month timeframe around each follow-up time-point for returning the data is a reasonable estimate for a participant to attend a follow-up appointment and complete/return the questionnaire. The primary analysis model will be repeated, firstly with participants that had completed their follow-up questionnaire within a window of one month either side the follow-up time points (i.e. 5-7 and 11-13 months post-randomisation respectively). This analysis will then be repeated but with a two-month window either side of the follow-up time-points.

If the planned primary analysis is not severely mis-specified, then we will repeat the primary analysis, but include the follow-up times as a continuous predictor, measured in weeks (as opposed to the binary time point indicator used for the primary analysis). Follow-up time will be modelled using a restricted cubic spline with three knots placed at the 10th, 50th and 90th percentiles of the observed values. As for the primary analysis, the effects of time will be allowed to vary across randomised groups (via interaction between the spline terms for time and the treatment group indicator). The fitted model will be used to estimate and plot the differences in RCADS score between groups over the whole follow-up period, together with

a two-sided 95% confidence band (based on a t-distribution with degrees of freedom calculated using the method of Kenward and Roger).

5.8.4 Subgroup Analyses

The primary analysis will be repeated for each subgroup. The subgroup analyses models will use the primary analysis model with an additional interaction term between treatment group and respective subgroup. The corresponding p-value will be presented, alongside descriptive summaries of the primary outcome for each combination of the treatment group and subgroup.

Subgroup analyses will be carried out for the following subgroups:

5.8.4.1 Age

Two groups will be defined as less than 16 years old, and 16 years and older. We predict that participants 16 years and older may benefit more as could be seen as having a greater sense of values as they have had more years of development. Older participants may also have greater skills that complement the intervention such as organisational skills, which are involved in activity scheduling.

5.8.4.2 Gender

Two groups will be defined as males and females. We predict that females will benefit more with the intervention compared to males because the stigma is stronger with young men, particularly within a school setting.

5.8.4.3 Baseline RCADS-25 depression subscale

Two groups will be defined as low and high severity as defined by the RCADS outcome. We predict there to not be much difference between the groups however meta-analyses in previous literature have shown a greater effect size for those with more severe symptoms.

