3.4.3 Other Collected Data

- **Screening CRF**
 - PHQ-9A:
 - items 1-9
 - supplementary items 10-13 (risk questions)
 - total raw score
 - Date of screening
 - Inclusion criteria:
 - Aged between 12-18 years of age.
 - Scored at least 65 on the RCADS Depression Subscale.
 - Scored at most 14 on the PHQ-9A and did not answer risk questions in the affirmative (if scored greater than 14 – attends a secondary eligibility assessment with clinical member of the ComBAT team).
 - Exclusion criteria:
 - Young person eligible for secondary care CAMHS
- **Screening log**
 - Young person's initials (ID given if randomised)
 - Site name
 - Site ID
 - Name of location young person referred from:
 - Child and Adolescent Mental Health Services (CAMHS) name
 - Charity/Service name
 - School name
 - Referring professional
 - Research assistant
 - Date expression of interest received
 - Date of screening
 - RCADS Depression subscale score (as determined by screening CRF)
 - PHQ-9A score (as determined by screening CRF)
 - Young person eligible
 - Clinician follow-up call
 - Reason for screen failure/reason for ineligibility
 - Young person contacted for consent
 - Young person consented
 - Reason for non-consent
 - Additional notes

- **Baseline CRF**
 - Participant ID
 - Date completed
 - Date of birth
 - Gender
 - Ethnicity
 - Religion
 - Current living status
 - Living with parents, friends, alone, etc.
 - Number of people living in the same household
 - Number of people under 18 in the same household
 - Current education status
 - In education
 - Type of education
 - Employment status
 - Preference of support delivery
- **Therapist Demographic Information**
 - Therapist initials
 - Role (e.g. Child wellbeing practitioner, Nurse, Counsellor)
 - Grade
 - Organisation
 - Age (Grouped)
 - Gender
 - Time working with young people
 - Approaches used when supporting young people
- **Session record (behavioural activation)**
 - Participant ID
 - Date completed
 - Location of session (online, telephone, in person)
 - Professional's name
 - Session recorded
 - Adverse events
 - Anyone else present (parent, sibling etc.)
 - Type of session (assessment, intervention, or review)
 - Strategies used during the session
 - Time spent preparing the session (mins)
 - Length of session (mins)
 - Time spent on administration after the session (mins)
- **Session record (usual care)**
 - Participant ID
 - Date completed
 - Location of session (online, telephone, in person)

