5.2.1 RCADS-25

The 25 items of the RCADS questionnaire are scored from 0-3. The 25 items are split into two sub-scales: anxiety scale (15 items) and depression scale (10 items). The raw scores for each sub-scale will be calculated and then an overall score will be calculated.

The total raw scores and overall raw score will be converted into T-scores (further details of conversions in Section 5.3.1 below). Higher t-scores denote greater clinical need. The t-scores will be arranged into the following clinical cut-offs: 0-64 non-clinical range, 65-69 borderline clinical range, and ≥ 70 clinical range.

For missing data, mean imputation will be used when at most three items are missing from the anxiety sub-scale and at most two items are missing for the depression sub-scale. If the child's date of birth/age is missing and/or the child's sex is missing, selected as 'Non-binary' or 'Prefer not to say', the RCADS-25 T-Score cannot be calculated.

Guidance for calculating T-scores and missing data refers to the RCADS-25 Child Version Scoring Program 3.1 (Ebesutani et al (2012)).

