5.3 Derivation of Variables and Outcomes

5.3.1 RCADS T-scores

The RCADS T-scores are derived by transforming the raw scores depending on sex and the grade they are in at school. As UK schools do not use grades, the young person's age will be used to approximate their school grade. This will be approximated by adding 6 to the young person's age as suggested by the RCADS-25 Child Version Scoring Resources (Ebesutani et al (2012)). Table 2 shows the specific transformations for each permutation of sex and age.

Table 2: RCADS raw score transformations to derive T-scores for each sub-scale and overall.

Sex	Age (Grade)	Depression T-score	Anxiety T-score	Overall T-score
Male	10 (4)	$((Score - 9.90)*10)/4.93 + 50$	$((Score - 15.19)*10)/7.09 + 50$	$((Score - 25.10)*10)/11.10 + 50$
	11-12 (5-6)	$((Score - 7.13) *10)/4.22 + 50$	$((Score - 11.63)*10)/6.45 + 50$	$((Score - 18.76)*10)/9.38 + 50$
	13-14 (7-8)	$((Score - 7.56) *10)/3.75 + 50$	$((Score - 10.48)*10)/5.36 + 50$	$((Score - 18.04)*10)/7.92 + 50$
	15-16 (9-10)	$((Score - 7.50) *10)/4.18 + 50$	$((Score - 9.70)*10)/5.45 + 50$	$((Score - 17.20)*10)/8.53 + 50$
	17-18 (11-12)	$((Score - 7.64) *10)/4.37 + 50$	$((Score - 9.96)*10)/4.32 + 50$	$((Score - 17.60)*10)/7.24 + 50$
Female	10 (4)	$((Score - 9.68)*10)/4.97 + 50$	$((Score - 16.25)*10)/8.42 + 50$	$((Score - 25.93)*10)/12.24 + 50$
	11-12 (5-6)	$((Score - 8.03)*10)/5.00 + 50$	$((Score - 13.49)*10)/7.62 + 50$	$((Score - 21.53)*10)/11.73 + 50$
	13-14 (7-8)	$((Score - 8.08)*10)/4.34 + 50$	$((Score - 12.74)*10)/6.22 + 50$	$((Score - 20.82)*10)/9.46 + 50$
	15-16 (9-10)	$((Score - 8.14)*10)/4.37 + 50$	$((Score - 11.31)*10)/5.33 + 50$	$((Score - 19.45)*10)/8.63 + 50$
	17-18 (11-12)	$((Score - 8.59)*10)/3.67 + 50$	$((Score - 11.50)*10)/5.34 + 50$	$((Score - 20.09)*10)/7.79 + 50$

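### Effect modification by age and baseline depression severity is tested only through two-group splits of scaled variables, and the severity cut is not stated

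*SAP*

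**What the plan says.** Section 5.8.4 repeats the primary model for each subgroup "with an additional interaction term between treatment group and respective subgroup" and reports the p-value of that term with descriptive summaries.

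- Age (5.8.4.1): "Two groups will be defined as less than 16 years old, and 16 years and older".
- Baseline depression severity (5.8.4.3): "Two groups will be defined as low and high severity as defined by the RCADS outcome". No cut-point follows.

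No interaction with either variable in continuous form is planned. Both exist on a scale: age is derived from date of birth (5.3.2), and the depression subscale has 10 items scored 0-3 (5.2.1), converted to a T-score by Table 2 (5.3.1).

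Two other places bear on the severity split. The inclusion criteria in 3.4.3 include "Scored at least 65 on the RCADS Depression Subscale"; this must be a T-score, since the raw subscale cannot exceed 30. The only RCADS bands in the SAP are in 5.2.1: "0-64 non-clinical range, 65-69 borderline clinical range, and ≥ 70 clinical range".

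**The concern.** Replacing a scaled modifier by a two-group indicator discards the variation within each group. If the treatment effect changes steadily with the modifier, the interaction test loses power for nothing in return. Interaction tests are already weak in a trial sized for a main effect.

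Severity is the more exposed of the two. Entry at T = 65 or above empties the non-clinical band at screening, so the one remaining band limit, 70, lies only five T-points above the floor. Because 5.8.4.3 names no cut, the choice of split is also still open, and different choices can give different p-values. Section 5.8.4.3 itself notes that earlier meta-analyses found larger effects in more severe cases, although its own prediction is of little difference.

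**Working it through.** **Plan's own figure.** Section 3.5 sizes the trial at 86 per group for 90% power at d = 0.5. A two-sided 5% t-test with 86 per group has power 0.903, so this reproduces. The SAP gives no power for subgroup tests. From its recruitment target, 23% loss and design effect, the effective number is 236 × 0.77 / 1.04 ≈ 175.

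**Width of the low severity group if the cut is 70.** Table 2 gives T = (raw − m) × 10 / s + 50, so T = 65 at raw = m + 1.5s and T = 70 at raw = m + 2s. For girls aged 17-18, with "Score - 8.59)*10)/3.67 + 50": 8.59 + 1.5 × 3.67 = 14.10 and 8.59 + 2 × 3.67 = 15.93, so 15 is the only whole raw score between them. The maximum raw score is 30.

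| Band | Raw at T=65 | Raw at T=70 | Raw scores, 65 ≤ T < 70 | Raw scores, T ≥ 70 |
|---|---|---|---|---|
| Male 11-12 | 13.46 | 15.57 | 14-15 | 16-30 (15) |
| Male 13-14 | 13.19 | 15.06 | 14-15 | 16-30 (15) |
| Male 15-16 | 13.77 | 15.86 | 14-15 | 16-30 (15) |
| Male 17-18 | 14.20 | 16.38 | 15-16 | 17-30 (14) |
| Female 11-12 | 15.53 | 18.03 | 16-18 | 19-30 (12) |
| Female 13-14 | 14.59 | 16.76 | 15-16 | 17-30 (14) |
| Female 15-16 | 14.70 | 16.88 | 15-16 | 17-30 (14) |
| Female 17-18 | 14.10 | 15.93 | 15 | 16-30 (15) |

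The low group spans 1 to 3 raw scores with unrounded T. If T is rounded to whole numbers first, it spans 2 to 3 in every band. Without a rounding rule, boys of 13-14 with raw 15 (T = 69.8) and girls of 11-12 with raw 18 (T = 69.9) lie between the stated bands.

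**Information kept by the severity cut.** For a linear interaction, the share kept is the squared correlation r² between the score and its indicator. The SAP gives no baseline distribution, so I assume a normal score truncated at 65. Let a = (65 − μ)/σ and c = (70 − μ)/σ. Let λ(x) be the normal density at x divided by the upper tail beyond x, and p the share at or above 70. Then

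r² = p (λ(c) − λ(a))² / [(1 − p)(1 + aλ(a) − λ(a)²)].

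For 70/8: p = 0.681, λ(c) = 0.798, λ(a) = 0.447, variance term 0.521, so r² = 0.681 × 0.351² / (0.319 × 0.521) ≈ 0.50.

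| Mean/SD before truncation | Share in high group | Information kept |
|---|---|---|
| 65/8 | 53% | 59% |
| 70/8 | 68% | 50% |
| 75/10 | 82% | 36% |
| 78/10 | 87% | 30% |

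For comparison, a median split of an untruncated normal score keeps 2/π = 64%.

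**Baseline scores below 65.** If the baseline score is a fresh measurement correlated 0.7 to 0.9 with screening (assumed), simulation puts 8-14% below 65 for 70/8 and 3-6% for 78/10. The cut at 70 then keeps about 55-60% and 35-42% respectively, against 50% and 30% above.

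**Information kept by the age cut.** For age uniform over completed years 12-18, the share aged 16 and over is 3/7, and r² = 3p(1 − p) = 3 × (3/7) × (4/7) = 0.735. Other readings of the age range give 67% (12 to exactly 18) to 75% (whole years only).

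**Detectable binary interaction.** With n = 175 and low share q, SE = √(4/(nq) + 4/(n(1 − q))) in SD units, and the 80% power threshold is 2.80 × SE: 0.85 SD for a 50/50 split, 1.06 SD for 20/80 and 1.41 SD for 10/90, before any gain from covariate adjustment.

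**The case against.** The strongest reply is that the SAP does not commit to a cut at 70. A reader might infer that 65-69 against 70 and over is the only split its bands allow, but the document does not support that. Section 5.8.4.3 states no number, and the floor of 65 is applied at screening (3.6), while 3.4.1 lists the RCADS-25 as collected at baseline. A baseline score can fall below 65, so the low group need not be confined to a few raw scores. This stands, and it is why the width and the loss are given conditionally.

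A reader might also infer that the test sets a thin slice against nearly everyone else. The count of raw scores is not a share of participants. The trial recruits mild to moderate depression (3.2), so scores near the floor are plausible; with 65/8 the low group is 47% of the sample and the cut keeps about 59%. This stands too.

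For age, the cut is pre-specified with a direction and a rationale, and if the effect really steps at 16 the indicator is the efficient choice. That is fair: the squared correlation measures loss only under a linear interaction. But the rationale in 5.8.4.1, greater maturity and organisational skill with more years of development, describes a gradual change as readily as a step.

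Pre-specified categorical subgroups are common practice, and nothing here alters the primary estimate. None of this removes the core point: even a well-placed median split gives up about a third of the information.

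**Conclusion.** The point holds as a modest improvement to secondary analyses. Age and baseline depression severity are tested only as two-group modifiers, and the severity cut is undefined. If T = 70 is used, the loss for severity is about 40% to 70% under the assumed truncated normal distributions, and usually somewhat less if baseline scores drop below the floor. For age it is about a quarter (25-33% across readings of the age range). These figures assume a linear interaction and distributions that the SAP does not supply. They do not show that the subgroup tests are invalid or that the primary comparison is affected.

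**What to change.** In 5.8.4.1 and 5.8.4.3, base the interaction test on continuous terms:

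- Age in years by treatment, reported as the change in treatment effect per year with 95% CI.
- Baseline depression T-score by treatment, with the T-score also entered as a main effect, because the primary model adjusts for the baseline RCADS-25 and does not name the depression subscale as a term. Report the change in treatment effect per 5 T-points with 95% CI.

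Keep two-group summaries for display only: under 16 against 16 and over, and baseline depression T below 70 against 70 and over. Use unrounded T, so that no score falls between the groups or below the low group. Settle this before outcome data are seen by arm.

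The cost is a change of SAP wording within the same mixed-model framework; 5.8.3 already plans a continuous predictor interacting with treatment. The downside is the assumed linear interaction, which the grouped display helps to check.
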